### 17.2 Diagnosis Versus Signs and Symptoms

If known, a diagnosis should be recorded on the CRF rather than individual signs and symptoms (e.g., record only liver failure or hepatitis rather than jaundice, asterixis, and elevated transaminases). However, if a constellation of signs and/or symptoms cannot be clinically characterized as a single diagnosis or syndrome at the time of reporting, each individual event should be recorded as an AE or SAE on the CRF. If a diagnosis is subsequently established, it should be reported as follow-up information.

Roswell Park Protocol No.: I-659920

### **17.3 Adverse Events Occurring Secondary to Other Events**

In general, AEs occurring secondary to other events (e.g., cascade events or clinical sequelae) should be identified by their primary cause. For example, if severe diarrhea is known to have resulted in dehydration, it is sufficient to record only diarrhea as an AE or SAE on the CRF.

However, clinically significant AEs occurring secondary to an initiating event that are separated in time should be recorded as independent events on the CRF. For example, if a severe gastrointestinal hemorrhage leads to renal failure, both events should be recorded separately on the CRF.

### **17.4 Abnormal Laboratory Values**

Only clinically significant laboratory abnormalities that require active management will be recorded as AEs or SAEs on the CRF (e.g., abnormalities that require study drug dose modification, discontinuation of study treatment, more frequent follow-up assessments, further diagnostic investigation, etc.).

If the clinically significant laboratory abnormality is a sign of a disease or syndrome (e.g., alkaline phosphatase and bilirubin 5 x the upper limit of normal associated with cholecystitis), only the diagnosis (e.g., cholecystitis) needs to be recorded on the Adverse Event CRF.

If the clinically significant laboratory abnormality is not a sign of a disease or syndrome, the abnormality itself should be recorded as an AE or SAE on the CRF. If the laboratory abnormality can be characterized by a precise clinical term, the clinical term should be recorded as the AE or SAE. For example, an elevated blood potassium level of 7 mEq/L should be recorded as “hyperkalemia”.

Observations of the same clinically significant laboratory abnormality from visit to visit should not be repeatedly recorded as AEs or SAEs on the CRF, unless their severity, seriousness, or etiology changes.

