Cytokine Release Syndrome	≥ Grade 2, based on the Penn scale (45)	Permanently Discontinue	Permanently Discontinue	In discussion with the primary oncologist, tocilizumab, corticosteroids, and potentially other immunomodulators will be used based on clinical judgement for ARDS and CRS-like complications.

 Transient neutropenia is known to occur with rIFN- $\alpha$  and may reflect increased neutrophil migration to sites of infection or the tumor microenvironment as well as the effect of IFN- $\alpha$  on neutrophil survival and lifespan (46). This transient neutropenia has not been associated with an increased risk of infection.

 Refer to: <https://www.ncbi.nlm.nih.gov/pmc/articles/PMC5833070/> (Porter D, Frey N, Wood PA, Weng Y, Grupp SA. Grading of cytokine release syndrome associated with the CAR T cell therapy tisagenlecleucel [published correction appears in J Hematol Oncol. 2018 Jun 13;11(1):81]. J Hematol Oncol. 2018;11(1):35. Published 2018 Mar 2. doi:10.1186/s13045-018-0571-y].

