#### **10.2.2 Definition of DLT**

Treatment-related DLTs will be defined as the following events that occur between Day 1 to Day 7 that are considered possibly, probably, or definitely treatment-related:

- Grade 4 hematologic toxicity.
- Grade 3 hematologic toxicity with exception of transient leukopenia, neutropenia, lymphopenia, thrombocytopenia without bleeding, or anemia lasting 7 days or less.
- Grade 4 non-hematologic toxicities, with exception of asymptomatic increased LDH or lipase or amylase.
- Grade 3 non-hematologic toxicities with exception of nausea, vomiting, diarrhea, or flu-like symptoms that are controlled by optimal supportive management.

Distinguishing clinical manifestations of COVID-19 from treatment-related DLT can be difficult because they can overlap. Manifestations of COVID-19 present at baseline (e.g., fever, shortness of breath) that are unchanged after the study regimen is begun will not be considered DLT. Worsening of these manifestations can be due to COVID-19 or treatment-related, and unless there is a specific well defined unrelated cause, all AEs that are at least possibly related to the study regimen that meet one of the criteria for DLT based on CTCAE severity will be considered DLT.

In patients who received recent chemotherapy, radiation, and/or immunotherapy toxicities from recent chemotherapy would be known to the primary oncologist, and we would interpret AEs attributed to the study regimen with this knowledge in mind. For example, if a patient received cytotoxic chemotherapy known to cause leukopenia prior to development of COVID-19, development of leukopenia following initiation of study therapy will not be considered treatment-related, depending on the expected degree and duration of leukopenia following chemotherapy.

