#### **10.2.3 Toxicity Management**

The toxicity of high dose interferon (20 million units/m^2/d) has been established by Kirkwood et al in a number of trials. Most notable was the E1684 trial (47) where HDI (20 million units/m^2/d) was administered daily for 5 days x 4 weeks. In that trial (n=143), grade 3 toxicities were 67%, grade 4 toxicities were 9% (mainly constitutional and neurologic), and there were 2 treatment related mortalities (grade 5) due to hepatotoxicity. The proportion of Grade 3 and 4 toxicities in that trial were 48.2% for constitutional toxicities (defined as ‘worst grade of any constitutional toxicity, including fever, chills, flu-like symptoms, fatigue, malaise, and diaphoresis), and 66% for non-constitutional toxicities (23.8% for myelosuppression, 13.9% for hepatotoxicity, 28% for neurological toxicity).

Roswell Park Protocol No.: I-659920

While the combination of HDI and rintatolimod may lead to synergistic additive side effects, we will monitor subject toxicities for unexpected increases in constitutional symptoms, myelosuppression, hepatotoxicity, and neurological toxicity. We will focus on monitoring for grade 3 or greater treatment related hematologic toxicities, and grade 4 or greater treatment related non-hematologic toxicities. A non-informative prior distribution of SAEs will be utilized to develop the safety stopping rules (details in Section 19).

To our knowledge, the combination of HDI and rintatolimod has not been tested previously in patients with COVID-19. Therefore, we may observe adverse events that were not observed in trials of cancer and specific adverse events may be more severe in patients with COVID-19. One possibility is worsening of acute lung injury or systemic inflammatory response. Though the protocol does not specify specific treatments for such AEs, agents used for cytokine release syndrome, e.g. Tocilizumab, or JAK2, TNF $\alpha$ , IL-1 inhibitors, may be used, based on physician judgment.

- **Gastrointestinal Toxicity**

- Nausea and/or vomiting should be controlled with adequate antiemetic therapy. Prophylactic antiemetic therapy can be used at the discretion of the investigator/sub-investigator. Subjects are encouraged to take plenty of oral fluids.

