## 17 SAFETY EVALUATION

### 17.1 Adverse Events

An adverse event or adverse experience (AE) is any untoward medical occurrence associated with the use of a drug in humans, whether or not considered drug related. Therefore, an AE can be ANY unfavorable and unintended sign (including an abnormal laboratory finding), symptom, or disease temporally associated with the use of a medicinal (investigational) product, whether or not considered related to the medicinal (investigational) product (attribution of ‘unrelated’, ‘unlikely’, ‘possible’, ‘probable’, or ‘definite’).

An AE is considered “unexpected” if it is not listed in the investigator brochure or is not listed at the specificity or severity that has been observed; or if an investigator brochure is not required or available, is not consistent with the risk information described in the general investigational plan in other study-related documents.

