### **Primary Endpoint**

- The primary safety endpoint is the frequency of grade 3 or 4 AEs considered to be possibly, probably, or definitely related to the treatment regimen.

**Phase IIa.** The Phase IIa component of the trial is designed to be a single arm trial of IFN $\alpha$  (at MTD, if reached, otherwise at 20 MU/M) + rintatolimod along with the best available standard of care. Using each patient's baseline nasopharyngeal viral load, we will evaluate to what extent the study regimen reduces viral load relative historical institutional benchmarks. The sample size will be n=10.

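### Section 17.4 makes AE recording of laboratory values depend on active management, so Main Cohort grade 3-4 cytopenias first seen after the last dose can be left out of the primary safety endpoint

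*Combined protocol and SAP*

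**What the plan says.** Section 17.4 sets the recording rule: "Only clinically significant laboratory abnormalities that require active management will be recorded as AEs or SAEs on the CRF". It gives examples of what qualifies: "abnormalities that require study drug dose modification, discontinuation of study treatment, more frequent follow-up assessments, further diagnostic investigation, etc". Section 17.1 defines an AE without that condition: "an AE can be ANY unfavorable and unintended sign (including an abnormal laboratory finding").

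The Phase I primary safety endpoint in Section 19.1 is the "frequency of grade 3 or 4 AEs considered to be possibly, probably, or definitely related to the treatment regimen". The Phase IIa endpoint also counts grade 3-4 AEs, with a narrower attribution. Section 10.2.2 lists "Grade 4 hematologic toxicity" as a DLT between Day 1 and Day 7 if at least possibly related, with no condition on management and no exception for short duration. Section 10.2.3 adds: "We will focus on monitoring for grade 3 or greater treatment related hematologic toxicities".

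On neutropenia, Table 2 describes a transient fall as expected, and its footnote 1 says: "This transient neutropenia has not been associated with an increased risk of infection".

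**The concern.** The endpoint and the DLT list ask what grade an event reached. Section 17.4 asks whether anyone had to act on it. A grade 3 or 4 value on which nobody acts is not an AE on the CRF, and what is not an AE cannot enter a count of grade 3-4 AEs.

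At stake is a downward bias in the primary safety frequency, concentrated in blood counts and dependent on the judgement of an investigator who knows the treatment. If the DLT decision uses the same forms, one missing event could also change a 3+3 decision, because Section 19.2.1 adds three patients to a dose level after one DLT in three.

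**Working it through.** The plan gives no figure for this loss, so there is none to reproduce. The check sets the provisions side by side.

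**1. Is there another route into the endpoint?** None was found. The Phase 1 reporting grid in Section 17.6.2 covers all grades and attributions, but only of events already called AEs. Section 19.1 promises summaries and individual listings of all data. It does not say that laboratory values will be CTCAE-graded and added to the endpoint independently of the AE form.

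**2. When does dose action force recording?** Main Cohort dosing is Day 1 and Day 3 or 4 (Section 10.4). Section 10.1 requires acceptable laboratory results before each treatment. Hematology and chemistry follow Sections 11.1 and 11.2.

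| Scheduled draw | Doses reflected | Doses left to change | DLT window |
|---|---|---|---|
| Day 3 (+1), pre-dose | 1 | 1 | inside |
| Day 7 (±1) | 2 | 0 | nominally the last day |
| Day 14 (±3) | 2 | 0 | outside |

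At Day 3, Table 2 calls for action on grade 3 AST, ALT or bilirubin and on grade 3-4 neutropenia, and Section 10.2 stops therapy for any related grade 4 toxicity. Each is active management, so the event is recorded. At Day 7 and Day 14, the only scheduled draws that reflect both doses, no planned dose is left to hold, reduce or stop.

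**3. What else forces recording after the last dose?**

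- *AST, ALT, bilirubin.* Table 2 advises evaluation for other causes. That is further diagnostic investigation under Section 17.4 and does not need a remaining dose. These events are largely protected.
- *Neutropenia.* Table 2 calls for specialist consultation only when it is prolonged and not explained by the regimen or recent chemotherapy. Otherwise an investigator may reasonably decide that nothing is needed.
- *Thrombocytopenia, anemia, lymphopenia.* They have no row of their own. They fall in the catch-all row, which itself depends on a judgement of clinical significance. The grade 3 rule in Section 10.2.1 covers non-hematologic toxicity only. At grade 3 they depend on judgement even while doses remain.

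**4. DLTs.** The criteria in Section 10.2.2 are by grade, but its discussion of attribution refers to AEs that meet them. The plan does not say whether DLT review uses AE forms or laboratory results.

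**5. Sensitivity of the 3+3, illustration only.** Let p be the true DLT probability and c the fraction of DLTs captured. The value of c is an assumption; the documents give no basis for it. A level is passed with 0 of 3 DLTs, or with 1 of 3 followed by 0 of 3:

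P(pass) = (1−cp)³ + 3cp(1−cp)² × (1−cp)³

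For p = 0.33 and c = 1: 0.67³ + 3 × 0.33 × 0.67² × 0.67³ = 0.301 + 0.134 = 0.43.

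| p | c = 1 | c = 0.90 | c = 0.75 | c = 0.50 |
|---|---|---|---|---|
| 0.20 | 0.71 | 0.75 | 0.81 | 0.91 |
| 0.33 | 0.43 | 0.50 | 0.61 | 0.78 |

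Here c applies to all DLTs. Only laboratory DLTs that trigger no action are at risk, and only if review relies on AE forms, so the true c may be close to 1.

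**The case against.** The strongest reply is that the gate is wide. Section 17.4 counts extra follow-up and investigation as active management, Table 2 and Section 10.2 force action during dosing, and the hepatic work-up applies at any visit. DLTs are defined by grade, and the reference to AEs in Section 10.2.2 can be read with Section 17.1, where laboratory findings qualify. Blood is drawn at every visit and all data will be listed, so nothing is physically lost. Most of this stands. It removes the hepatic example almost entirely, as well as most of the Day 3 risk. It does not reach cytopenias first seen after the last dose, and a listing of values is not a count in the endpoint.

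A related reply is that a Day 7 cytopenia would need extra draws to settle whether it lasted more than seven days, which would itself trigger recording. The windows do leave the two visits 3 days (Day 8 to Day 11) to 11 days (Day 6 to Day 17) apart. But no provision requires those draws, and the duration exception concerns grade 3 only.

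Three stronger readings are tempting and not supported:

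- *That unmanaged grade 3-4 laboratory events in general drop out.* The action rules above prevent this for most events while dosing continues.
- *That Section 17.4 removes DLTs.* Short-lived grade 3 cytopenias and symptom-free grade 4 LDH, lipase or amylase rises are exempted on purpose in Section 10.2.2. Any other loss depends on how review is done.
- *That about half the endpoint is exposed.* In the interferon trial cited in Section 10.2.3, myelosuppression and hepatotoxicity make up 23.8 + 13.9 = 37.7 of 66 points of non-constitutional toxicity, or 57%. This omits the 48.2% constitutional toxicity; by the same crude addition the share is 37.7/(48.2 + 66) = 33%. Neither figure says what fraction would go unmanaged. That trial dosed daily for 5 days over 4 weeks, against two doses here, and the lowest Main Cohort tier receives no interferon.

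**Conclusion.** The concern holds in a limited form. Section 17.4 conflicts with Section 17.1 and does not match the grade-based endpoint and DLT list. The exposed events are Main Cohort grade 3-4 cytopenias first seen at Day 7 or Day 14, together with cytopenias that Table 2 does not name. The direction of bias in the primary frequency is downward; its size cannot be estimated from the documents. A missed Day 7 grade 4 hematologic DLT is possible only on the assumption that DLT review works from AE forms. The argument is weaker in the Expansion Cohort, where up to 12 infusions are allowed and later values can still affect dosing. Severity is moderate: the blood results will exist, but the plan does not say they will be graded and counted.

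**What to change.** Make three changes.

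1. In Section 17.4, state that any laboratory value of CTCAE v5.0 grade 3 or higher that is worse than the baseline grade, at any protocol draw, is recorded as an AE with grade and attribution whether or not it is managed. Keep the active-management condition for grades 1-2.
2. In Section 10.2.2 or 19.2.1, state that CBC and CMP results from Day 1 to Day 7 are screened for candidate DLTs, and that the existing attribution, duration, bleeding and exception criteria are then applied unchanged. Laboratory data alone cannot settle a DLT, because those criteria need clinical review.
3. Reconcile Sections 17.1, 17.4 and 10.2.2 so that they agree on when a graded laboratory value is an AE.

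The cost is about one paragraph and a few more AE entries from blood tests already scheduled, with a somewhat higher reported grade 3-4 frequency. No treatment rule changes.

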### **17.5 Preexisting Medical Conditions (Baseline Conditions)**

A preexisting medical condition should be recorded as an AE or SAE only if the frequency, severity, or character of the condition worsens during the study. When recording such events on an Adverse Event CRF, it is important to convey the concept that the preexisting condition has changed by including applicable descriptors (e.g., “more frequent headaches”).

### **17.6 Grading and Reporting Adverse Events**

#### **17.6.1 Grading and Relationship to Drug**

The descriptions and grading scales found in the CTEP Version 5.0 of the NCI Common Terminology Criteria for Adverse Events (CTCAE) will be utilized for AE reporting. CTEP Version 5.0 of the CTCAE is identified and located at:

[http://ctep.cancer.gov/protocolDevelopment/electronic\\_applications/ctc.htm](http://ctep.cancer.gov/protocolDevelopment/electronic_applications/ctc.htm).

AEs not covered by specific terminology listed should be reported with common medical terminology and documented according to the grading scales provided in the CTCAE Version 5.0.

The relationship of event to study drug will be documented by the Investigator as follows:

**Unrelated:** The event is clearly related to other factors such as the participant's clinical state, other therapeutic interventions or concomitant drugs administered to the participant.

**Unlikely:** The event is doubtfully related to investigational agent(s). The event was most likely related to other factors such as the participant's clinical state, other therapeutic interventions, or concomitant drugs.

**Possible:** The event follows a reasonable temporal sequence from the time of drug administration but could have been produced by other factors such as the participant's clinical state, other therapeutic interventions, or concomitant drugs.

**Probable:** The event follows a reasonable temporal sequence from the time of drug administration and follows a known response pattern to the study drug. The event cannot be reasonably explained by other factors such as the participant's clinical state, therapeutic interventions, or concomitant drugs.

**Definite:** The event follows a reasonable temporal sequence from the time of drug administration, follows a known response pattern to the study drug, cannot be reasonably explained by other factors such as the participant's condition, therapeutic interventions or concomitant drugs; AND occurs immediately following study drug administration, improves upon stopping the drug, or reappears on re-exposure.

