## 2.3 Past experience with IFN $\alpha$ and Rintatolimod

**Interferon-alpha** (INTRON® A) is currently FDA approved for the adjuvant treatment of stage III melanoma. It has been examined by multiple investigators as an immune modulator in the setting of vaccine therapy with demonstrated safety (15). It has been extensively evaluated in the setting of metastatic CRC (as single agent or in combination with chemotherapy or IL-2), but was

Roswell Park Protocol No.: I-659920

shown to be largely ineffective (16-33) at daily doses ranging from 3-20 million units/m^2, administered subcutaneously or intravenously. In the treatment of melanoma, a small study by Astsaturov and colleagues (34) administered IFN $\alpha$ -2b in previously vaccinated melanoma patients, and was shown to convert immunization into objective clinical responses, suggesting its ability to amplify the effectiveness of local T cells infiltration and/or function at the tumor site. Vaishampayan et al. examined IFN $\alpha$ -2b 5 million units subcutaneously three times a week following vaccination with a melanoma vaccine (Melaccine) (35). Treatment at this dose was well tolerated. Similarly Mitchell et al. recently completed a large trial examining IFN $\alpha$ -2b, 5 million units subcutaneously three times a week for one year (36). Di Pucchi and Pilla similarly examined the combination of a melanoma peptide vaccine with IFN $\alpha$ -2b, 3 million units subcutaneously three times a week, with little to no toxicity.

We propose to include a short course of high dose interferon alpha-2b (with the dose-escalation lead-in [0-5-10-20] and with maximum 20 million units/m^2, IV, on Days 1 and 3). The maximum dose of 20 million units/m^2 is similar or lower than the previously evaluated doses in melanoma patients (37-39). In this group of patients, in accordance with previous reports, we expect to consistently observe flu-like symptoms. However, this regimen hasn't been evaluated in patients with respiratory viral infection, and additional AEs may be observed. Specifically, augmentation of innate immune responses may also worsen inflammatory lung injury in patients with COVID-19 infection, and therefore safety and efficacy are primary endpoints of this trial.

**Rintatolimod** (Selective toll-like receptor-3 [TLR3] Ligand; analog of poly IC with reduced toxicity for i. v. use).

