## **16 MEASUREMENT OF EFFECT**

### **16.1 Primary Endpoints**

- The **primary safety** endpoints are frequency of grade 3 or 4 AEs considered to be possibly, probably, or definitely related to the treatment regimen.
- Evaluate kinetics of viral load in nasopharyngeal swabs based on quantitative PCR in the course of treatment and Days 7, and 14.

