### **Primary Endpoint**

- Evaluate kinetics of viral load expressed as Ct values in nasopharyngeal swab samples over time measured at baseline (day 0), Days 3 (last day of treatment), 7, and 14 (40). The primary endpoint will be the area under the Ct curve (AUC).

The primary Phase IIa safety endpoint is the frequency of grade 3 or 4 AEs considered to be probably or definitely related to the treatment regimen.

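### The Phase IIa primary safety endpoint counts only probably or definitely related events, so most worsening lung injury is likely to be rated possible and left out

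*Combined protocol and SAP*

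**What the plan says.** The primary safety endpoint is defined in four places, with two different attribution thresholds.

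- Section 19.1, Phase IIa: "The primary Phase IIa safety endpoint is the frequency of grade 3 or 4 AEs considered to be probably or definitely related". Section 8.1, which is not limited to a phase, sets the same threshold.
- Section 19.1, Phase I: "The primary safety endpoint is the frequency of grade 3 or 4 AEs considered to be possibly, probably, or definitely related".
- Section 16.1, also not limited to a phase: "frequency of grade 3 or 4 AEs considered to be possibly, probably, or definitely related to the treatment regimen".

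Section 17.6.1 defines the ratings. An event is *possible* if its timing fits but it "could have been produced by other factors such as the participant's clinical state". It is *probable* only if it matches a response already known for the drug and, in addition, "The event cannot be reasonably explained by other factors". *Definite* keeps both conditions and adds a further one: immediate onset, improvement on stopping, or recurrence on re-exposure.

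The reason for making safety primary is given in Section 2.3: "augmentation of innate immune responses may also worsen inflammatory lung injury in patients with COVID-19 infection, and therefore safety and efficacy are primary endpoints". Section 2.2 says much the same, and Section 10.2.3 repeats the risk and adds that, to the authors' knowledge, the combination is untested in COVID-19.

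On symptoms already present at baseline, Section 10.2.2 says: "Worsening of these manifestations can be due to COVID-19 or treatment-related". It then counts an event of DLT severity if it is at least possibly related, unless a specific and well-defined unrelated cause exists.

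**The concern.** The Phase IIa threshold works against the hazard that the endpoint was chosen to watch. Respiratory decline in a patient with COVID-19 usually has a ready alternative explanation, namely COVID-19. Under Section 17.6.1 that points to a rating of possible, and a possible event does not enter the endpoint as Sections 8.1 and 19.1 define it.

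A low Phase IIa count could then reflect how events were labelled rather than how often lungs worsened. Anyone carrying that figure forward to the larger randomized trial foreseen in Section 2.6 could read it as reassurance on lung injury that it cannot give.

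**Working it through.** The plan attaches no rate, limit or power to the Phase IIa safety endpoint, so there is no figure to reproduce. The check is mainly a comparison of texts, followed by an illustration of size.

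**Step 1. Which rules count a possible event?**

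| Place | Grade or severity | Possible events counted? |
|---|---|---|
| 8.1 (no phase stated) | 3–4 | No |
| 19.1, Phase IIa | 3–4 | No |
| 19.1, Phase I | 3–4 | Yes |
| 16.1 (no phase stated) | 3–4 | Yes |
| 10.2.2, DLT, Days 1–7 | listed grade 3 and 4 events | Yes |

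The plan gives no reason for the narrower Phase IIa rule. The Expansion Cohort lies outside the Phase IIa arm described in Section 19.1. Only Sections 8.1 and 16.1 reach it, and they disagree.

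**Step 2. What rating would lung worsening receive?** Both higher ratings require that the clinical state is not a reasonable explanation. The extra conditions for definite come on top of that requirement and do not replace it. What Section 10.2.2 says about worsening, that either the disease or the drug may be the cause, is close to the Section 17.6.1 definition of possible. The plan's own history points the same way. Section 13.2 reports that adverse events under an earlier rintatolimod and interferon combination, shortness of breath among them, were judged possibly related to the patients' condition and possibly to the drugs.

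**Step 3. Size, for illustration.** Inputs:

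- n = 10 Phase IIa patients (Section 19.1).
- p, the true proportion of patients with grade 3–4 lung worsening that is at least possibly related. The documents give no value; 10% and 20% are assumed.
- q, the share of those events rated probable or definite. Also assumed.

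Taking patients as independent, the chance of counting at least one event under the Phase IIa threshold is 1 − (1 − pq)^10. If possible events also count, it is 1 − (1 − p)^10.

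| | p = 10% | p = 20% |
|---|---|---|
| Possible events count | 1 − 0.90^10 = 65% | 1 − 0.80^10 = 89% |
| Not counted, q = 25% | 1 − 0.975^10 = 22% | 1 − 0.95^10 = 40% |
| Not counted, q = 0 | 0% | 0% |

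The expected numbers of affected patients are 10 × 0.10 = 1 and 10 × 0.20 = 2.

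**Step 4. What a zero would mean.** With 0 of 10 counted, the exact one-sided 95% upper limit is 1 − 0.05^(1/10) = 25.9%. That limit applies only to events rated probable or definite. It does not bound the rate of lung worsening rated possible.

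**The case against.** The case on the other side has five parts.

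1. **Attribution is a judgement.** Section 17.6.1 asks whether other factors *reasonably* explain the event, not whether COVID-19 conceivably could. Abrupt worsening tied to an infusion, easing when it stops, could be rated probable or definite. Section 13.2 already lists bronchospasm, chest tightness and shortness of breath with rintatolimod, so a known pattern is not excluded merely because the combination is new in COVID-19. Section 10 and the Expansion Cohort calendar foresee rising oxygen needs being attributed to rintatolimod. This stands, and it rules out any claim that such events can never be counted. It does not remove the tendency: the attribution level for oxygen needs is not stated, and a rating of possible would satisfy that text.

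2. **Section 16.1 counts possible events.** True, and if Section 16.1 governs, the omission disappears. But the phase-specific text in Section 19.1 says otherwise, and nothing says which prevails.

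3. **The events are captured elsewhere.** Ventilation and 30-day death are secondary endpoints whatever the attribution, as is hospitalization for patients not already admitted. Section 17.6.2 collects all grade 3–4 events, individual listings are planned, and the DSMC reviews safety. The DLT rule also screens dose levels before Phase IIa. All of this stands, so the harm would not go unseen. Still, for a patient already in hospital, worsening short of ventilation or death falls in none of the three clinical endpoints, and the 3+3 stage covers only the Main Cohort.

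4. **Leaving out background disease is the purpose of attribution.** This is fair, and it is why an all-cause count belongs beside the attributed one rather than in its place.

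5. **No decision hangs on the endpoint.** Correct. A reader might infer that the trial could declare the regimen safe on a zero count, but the plan sets no safety success rule.

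**Conclusion.** The point holds as a matter of likelihood. Under Sections 8.1 and 19.1, most worsening lung injury is likely to be rated possible and so left out of the Phase IIa primary safety endpoint. The defect is the probable/definite threshold. It conflicts with Section 16.1 and is narrower than both the Phase I endpoint and the DLT rule. The attribution scale itself is not at fault, since the same scale loses no possible events where they are counted.

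On the assumed rates, the chance of counting any such event among 10 patients falls from 65% or 89% to 22% or 40% if a quarter are rated higher, and to zero if none is. These figures rest on assumed values of p and q and show scale only.

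A reader might also apply the 40% rate of ventilation or death from Section 8.2 and conclude that about 4 of 10 patients would have an uncountable event. The documents do not support that. The 40% is an expected all-cause disease rate whose limitations Section 8.2 itself notes; it is not a rate of drug-caused injury. The Main Cohort excludes severe COVID-19 at entry (Section 3.2). Deaths fall outside the endpoint because it stops at grade 4, not because of attribution.

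**What to change.** - In Sections 8.1, 16.1 and 19.1, define the primary safety endpoint with one attribution threshold: possibly, probably or definitely related.
- Beside it, report descriptively the number of patients with grade 3 or higher respiratory and systemic-inflammatory adverse events regardless of attribution, with exact confidence intervals, for the Phase IIa and the Expansion patients. State that grade 3 or higher includes fatal events.

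The cost is endpoint and table wording. No new data are needed: Section 17.6.2 already collects grade 3–4 events at every attribution level, and deaths are recorded as serious adverse events under Section 17.7. The drawback is that both rates will be higher because they take in some COVID-19 progression. In a cohort without concurrent controls, the all-cause count cannot separate drug from disease, and the report should say so.
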